4.4.1.2 Unsolicited AEs

Unsolicited AEs includes both serious (SAEs) and non-serious unsolicited AEs.

4.4.1.2.1 Presence

An observation will be considered an event if it has at least a verbatim term and is not a Grade 0 intensity event.

Grade 0 events are not included in safety analysis but are included in separate listings.

4.4.1.2.2 Intensity

Intensity will be defined according to the following classification: None, Grade 1, Grade 2, Grade 3, or Missing.

If the unsolicited AE is measurable and its preferred term is part of the list of solicited reactions, then the measurement is derived based upon and following the same rule of the intensity scales defined in the **Error! Reference source not found.** and **Error! Reference source not found.** for that measurable injection site or systemic reaction. Note the intensity could be considered as "None" (not a reaction) in the analysis despite being considered a reaction by the investigator (e.g., swelling measurement >0 mm but < 25 mm in adults).

Intensity for the other unsolicited AEs will correspond to the value reported in the CRF.

The maximum intensity corresponds to the highest intensity for a unique term.

-
- Confidential/Proprietary Information
 - Page 49 of 67

4.4.1.2.3 Last Vaccination

Last vaccination before an unsolicited AE is derived from the start date of the unsolicited AE provided in the CRF and is calculated as follows:

- If an unsolicited AE has a complete start date and different to any of the vaccination dates, the start date is used to determine the last vaccination before the unsolicited AE
- If the start date is missing or partially missing, or equal to any vaccination date, then the visit number in the “Appeared after Visit” or similar field, is used to determine the last vaccination before the unsolicited AE.

4.4.1.2.4 Time of Onset

Time of onset is derived from the start date of the unsolicited AE and the date of last vaccination as described in Section **Error! Reference source not found.**:

Time of Onset = start date of the unsolicited AE – date of last vaccination before the unsolicited AE

The time of onset is considered as missing only if one or both of the dates are missing or partially missing.

The unsolicited AEs will be analyzed “Within 30 days” after each vaccination, which corresponds to AEs with a time of onset between 0 and 30 days after vaccination or missing. An AE with missing time of onset will be considered to have occurred just after the last vaccination (computed according to the section **Error! Reference source not found.**), so will be included in these tables.

Time of onset period is displayed as D0-D3, D4-D7, D8-D14, D15 or later, and Missing.

Note: Unsolicited AE that occurred before vaccination (negative time of onset) or with a time of onset higher than defined above will not be included in analysis but will be listed separately.

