  - a. Review the diary card including any AEs, medications, or therapy that occurred since the last visit.
  - b. Ask the subject's parent / guardian if the subject has experienced any SAE in the time since vaccination that has not been reported to the study personnel. If an SAE, including an AESI, has occurred, follow the instructions in [Section 10](#) for reporting it.
  - c. Make arrangements to retrieve the diary card.

Visit 5 (5 months [+14 days] after Visit 4): Collection of Safety Information and Vaccination

- 1) If the diary card information from D0 to D07 (DC4) has not yet been obtained, obtain it at this time. Collect and review the pages of the diary card with the parent / guardian, including any AEs, medications, or therapy that occurred since vaccination. If an SAE, including an AESI, has occurred, follow the instructions in [Section 10](#) for reporting it.
- 2) Review the subject's relevant health history with parent / guardian, including any AEs, medications, or therapy that occurred since vaccination.
- 3) Review warnings and precautions to vaccinations.
- 4) Review contraindications to subsequent vaccinations.
- 5) Review conditions for withdrawal.
- 6) Contact IRT system for dose number for all vaccines to be given.
- 7) Administer the appropriate study vaccine per Operating Guidelines. Each vaccine should be administered in an assigned location and documented appropriately:
  - Meningococcal vaccine: inject IM into the anterolateral area of the thigh (preferably the right thigh).a,b
  - Prevnar 13®: inject IM into the anterolateral thigh (preferably the left thigh).a
  - M-M-R®II inject SC into the outer aspect of the upper arm (preferably the left arm)
  - Hexacima®: inject IM into the anterolateral area of the upper thigh (preferably the left thigh)
- 8) Keep the subject under observation for 30 minutes and record any AE in the source document.
- 9) Give the parent / guardian a diary card (DC5).
- 10) Remind the parent / guardian to expect a telephone call 8 days after Visit 5 and to bring back the diary card when they return for Visit 6 at a specified date and time.
- 11) Remind the parent / guardian to notify the site in case of an SAE.
- 12) Complete the relevant CRFs for this visit.

---

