4.3.2.2 Safety Endpoints

The observational endpoints for the evaluation of safety are:

- Occurrence, nature (Medical Dictionary for Regulatory Activities [MedDRA] preferred term), duration, intensity, relationship to vaccination, and whether the event led to early termination from the study, of any unsolicited systemic AEs reported in the 30 minutes after each vaccination
- Occurrence, time of onset, number of days of occurrence, intensity, action taken, and whether the reaction led to early termination from the study, of solicited (prelisted in the subject's diary card and CRF) injection site reactions occurring up to D07 after each vaccination
- Occurrence, time of onset, number of days of occurrence, intensity, action taken, and whether the reaction led to early termination from the study, of solicited (prelisted in the subject's diary card and CRF) systemic reactions occurring up to D07 after each vaccination
- Occurrence, nature (MedDRA preferred term), time of onset, duration, intensity, action taken, relationship to vaccination, and whether the event led to early termination from the study, of unsolicited AEs up to D30 after each vaccination
- Occurrence, nature (MedDRA preferred term), time of onset, duration, seriousness criteria, relationship to vaccination, outcome, and whether the event led to early termination from the study, of SAEs (including AESIs) throughout the trial from D0 to the last study visit

Assessment Methods

At each vaccination visit, the Investigator or a delegate will perform a physical examination on the basis of relevant medical history according to the Investigator's clinical judgment and will ask the parent / guardian about any solicited reactions and unsolicited AEs recorded in the diary card, as well as about any other AEs that may have occurred since the previous visit. All relevant data will be transcribed into the CRB according to the instructions provided by the Sponsor.

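### Unsolicited AEs with a partial start date are counted as within 30 days of vaccination even when the known month and year put onset after D30

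*SAP*

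**What the plan says.** The safety endpoint in SAP 4.3.2.2 concerns the occurrence "of unsolicited AEs up to D30 after each vaccination".

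SAP 4.4.1.2.4 defines onset as start date minus the date of the last vaccination. "The time of onset is considered as missing only if one or both of the dates are missing or partially missing". The 30-day analysis then takes in more than days 0 to 30: "which corresponds to AEs with a time of onset between 0 and 30 days after vaccination or missing". The reason given is an imputation: "An AE with missing time of onset will be considered to have occurred just after the last vaccination". By contrast, a completely dated late event, that is, one "with a time of onset higher than defined above will not be included in analysis but will be listed separately", stays out of the tables. The onset breakdown has its own row for missing values.

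SAP 4.4.1.2.3 chooses the vaccination to which the event belongs. "If the start date is missing or partially missing, or equal to any vaccination date", the visit number in the 'Appeared after Visit' or "similar field, is used to determine the last vaccination before the unsolicited AE". The SAP makes no other use of that field.

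SAP 4.4.1.3 and 4.4.1.4 tabulate SAEs and AESIs within 7 days, within 30 days and during the whole study. They do not say how a missing onset is handled in the two shorter periods.

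**The concern.** Counting a wholly undated event as early is a reasonable worst-case convention. The same rule is applied to dates that are only partly missing, where the known part may rule out the window. Two events with the same timing are then handled differently according to how fully the date was written: one is tabulated, the other only listed. The 30-day tables would contain events that cannot meet the definition of the endpoint they report. What is at stake is the accuracy of descriptive D0-D30 rates by dose and for any dose. No hypothesis test depends on them.

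**Working it through.** The plan states no figure to reproduce here, so the check applies the rule to test dates. The dates are assumed; the visit intervals come from Protocol 5.1.4.

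**Formula.** Earliest possible onset = first calendar day compatible with the recorded date parts, minus the date of the last vaccination. The window is excluded if the result exceeds 30.

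**Case 1: the month excludes the window.** The last vaccination is the 6-month dose, on 1 March; the start is recorded as June of the same year.
- Earliest onset: 31 (March) + 30 (April) + 31 (May) = day 92.
- Latest onset: 92 + 29 = day 121.
- The next vaccination is due 30 days plus 5 months after the 6-month dose, about the end of August, so June does fall in this gap.
- SAP rule: the onset is missing and the event is counted within 30 days. With any complete June date it would be excluded and listed.

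**Case 2: a shorter gap (Mexico).** Visit 1 vaccination on 10 January of a leap year; the start is recorded as March, appearing after Visit 1.
- Earliest onset: 21 (rest of January) + 29 (February) + 1 = day 51.
- Visit 2 is on day 60 to 74, so the event lies after D30 and before the next dose.
- SAP rule: counted within 30 days.

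**Case 3: the month does not exclude the window.** Vaccination on 10 January of a leap year; the start is recorded as February.
- Onset lies between day 22 (21 + 1) and day 50 (21 + 29).
- D30 is inside that range, so counting the event as early is a fair worst case. The rule should stay here.

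**The visit field.** Mexico Visit 4 and Russia Visit 5 have no vaccination and fall 30 to 44 days after the 6-month dose. If the field can hold such a visit, an event appearing after it starts on day 30 at the earliest. It is in the window only if the visit falls exactly on day 30 and the event starts that day. SAP 4.4.1.2.3 maps it to the 6-month dose, and 4.4.1.2.4 then counts it within 30 days.

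**Effect of one misplaced subject.** This assumes the planned group size as denominator and no other event for that subject in the table.

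| Group | n | 100/n (percentage points) |
|---|---|---|
| 1 | 200 | 0.50 |
| 2 | 100 | 1.00 |
| 3 | 150 | 0.67 |
| 4 | 75 | 1.33 |

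The documents give no count of partial dates, so the total effect cannot be computed.

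**The case against.** Several objections have force.

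- **Few late events may reach the database.** The procedures tables (SAP Tables 3.3 to 3.6) collect unsolicited AEs from D0 to D30 only, and SAP 4.3.2.3.3 tells parents to record events over a 30-day period. Other text disagrees: SAP 3.1 has recording continue to the next study visit, which is 60 to 74 days after the first two Mexico doses. At the Mexico visits in Protocol 5.1.4 the diary review also covers the interval broadly, "including any AEs, medications, or therapy that occurred since vaccination". SAEs are collected throughout the study, so late events remain possible on either reading.
- **Late SAEs are not lost.** A fully dated late SAE still appears in the during-the-study table. The unequal treatment concerns the 30-day tables only.
- **Data checks reduce partial dates.** Start dates are a required item, missing information must be explained, and data are queried and reviewed before lock. This lowers the number of incomplete dates but does not change the rule.
- **The rule is conservative, applies to all groups alike and is visible.** It resembles SAP 4.4.1.5.4, which counts a missing relationship as related. The row for missing onset shows how many events have no onset. It does not remove them from the 30-day counts, nor separate unknown dates from dates known to be late.

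Three stronger readings are tempting but unsupported. A reader might take the share of follow-up days outside every D0-D30 window as the share of incompletely dated events that are misplaced; that needs events to be collected evenly over follow-up, which the collection text contradicts. A reader might infer that rates are inflated in every group, or by some number of events per group; no document shows even one partially dated event. A reader might also take the visit number as proof of late onset; the CRF is not in the documents, and the field may list vaccination visits only.

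**Conclusion.** The rule is wrong as written for partial dates whose known parts exclude D0-D30, and nothing else in the SAP or protocol corrects it. The partial-date argument rests on the text of SAP 4.4.1.2.4 alone. The argument from the visit number also requires that the CRF field can hold a non-vaccination visit. The effect is conditional on such events occurring. Their number is unknown and likely small, and the affected tables are descriptive. Severity is minor.

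**What to change.** Amend SAP 4.4.1.2.4 to read, in substance: *An unsolicited AE with a missing or partial start date is counted within 30 days of the last vaccination unless the known parts of the date show that the earliest possible onset is after D30; such AEs are listed separately. If the CRF visit field can hold a non-vaccination visit, the date of that visit is used as a bound in the same way. AEs with no usable date information remain counted within 30 days.*

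Apply the corresponding bound to the 7-day and 30-day periods in SAP 4.4.1.3 and 4.4.1.4; those SAEs and AESIs stay in the during-the-study tables.

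The cost is a short SAP edit and a few lines of programming, with no new data. The downside is a slightly less conservative count. Safety belongs to the first of the two analyses in SAP 5.7, so the wording should be settled before that lock.

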Recording of solicited injection-site and systemic reactions		X		X		X	X				X		
Recording of unsolicited AEs	Collected from D0 to D30 after each vaccination visit												
Reporting of SAEs / AESIs‡‡‡‡	To be reported throughout the study period												
Trial Termination													X

Abbreviations: V: Visit; TC: telephone call; D: Day; IRT: interactive response technology; AE: adverse event; SAE: serious adverse event; AESI: adverse event of special interest

\*This call is made 8 days after the respective vaccinations. If Day 8 falls on a weekend or holiday, the telephone call may be made on the following business day. During this telephone call, the staff will find out whether the subject experienced any SAEs (including AESIs) not yet reported and will remind the subject's parent/guardian to continue using the diary card, to bring the diary card to the study center at the next visit, and confirm the date and time of the next visit

†This call is made 14 days before V06 to remind the subject's parent(s) of the forthcoming visit. If the subject's participation is discontinued due to withdrawal of parental / guardian consent or for other reasons, the staff will check over the phone to see if the subject received any medications or treatments or experienced any SAEs (including AESIs) that have not yet been reported to the study personnel and will make arrangements to retrieve the diary card.

‡"2 months" means from the 2nd month after birth to the day before the 3rd month after birth (2 months to 2 months 29 days).

§ Medical history to include history of maternal immunization against tetanus.

\*\* The results of urine laboratory tests, performed for the subject in terms of routine practice, can be used, if the tests were done within 7 days before Visit 0. In this case, no urine sample will be collected at Visit 0.

†† Physical examination to be performed as per routine standard of care. Temperature needs to be measured before each vaccination and recorded in the source documents.

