  - b. Ask the subject's parents(s) if the subject has experienced any SAE in the time since vaccination that has not been reported to the study personnel. If an SAE, including an AESI, has occurred, follow the instructions in [Section 10](#) for reporting it.
  - c. Make arrangements to retrieve the diary card.

Visit 6 (5 months [+14 days] after Visit 5): Collection of Safety Information and Vaccination

- 1) If the diary card information from D0 to D07 (DC5) has not yet been obtained, obtain it at this time. Review the subject's relevant medical history with the parent / guardian, including any AEs, medications, or therapy that occurred since vaccination. If an SAE, including an AESI, has occurred, follow the instructions in [Section 10](#) for reporting it.
- 2) Review the subject's relevant medical history with the parent / guardian, including any AEs, medications, or therapy that occurred since vaccination.
- 3) Review warnings and precautions to vaccinations.
- 4) Review contraindications to subsequent vaccinations.
- 5) Review conditions for withdrawal.
- 6) Contact IRT system for dose number for all vaccines to be given.
- 7) Administer the appropriate study vaccine per Operating Guidelines. Each vaccine should be administered in an assigned location and documented appropriately.
  - **For Group 3 only:** Meningococcal vaccine: inject IM into the anterolateral area of the thigh (preferably the right thigh).a, b
  - **For Groups 3 and 4:** MMRb
- 8) Keep the subject under observation for 30 minutes and record any AE in the source document.
- 9) Give the parent(s) (DC6).
- 10) Remind the parent(s) to expect a telephone call 8 days after Visit 3 and to bring the completed diary card when they return for Visit 7 at a specified date and time.
- 11) Remind the parent(s) to notify the site in case of an SAE.
- 12) Complete the relevant CRFs for this visit.

Telephone Call 5 (8 [+2] days after Visit 6)

Refer to steps in Telephone Call 1.

Visit 7 (30 [+14] days after Visit 6): Collection of Safety Information, Blood Sampling, and Trial Termination

---

a The only other vaccine that can be administered with the meningococcal vaccine in the right thigh is ENGERIX-B®. Do not administer Pentaxim® or PREVENAR 13® in the right thigh.

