### ***For the Russian Federation Only***

Any clinically significant abnormal results of the Visit 0 CBC, blood chemistry, or urinalysis according to Investigator's judgment will be reported as medical history. All laboratory tests will be sampled and analyzed locally. Results of the lab tests will be assessed by the Investigator. The Investigator should choose to not include the subject in the study if any of these laboratory tests have the potential to impact the health of the subject after vaccination. The laboratory values for CBC, blood chemistry, and urinalysis will only be collected in the CRF if they are clinically significant. Visit 0 laboratory tests are to be considered clinically significant in the following circumstances:

- Symptomatic
- Requiring corrective treatment or additional consultation by relevant specialist
- Leading to study vaccine discontinuation or postponing vaccination
- Meet SAE criteria

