### 9.3.3 Biological Laboratory Safety Assessment Methods (Sites in the Russian Federation Only)

Biological safety tests (biochemistry and hematology) will be performed at the study center’s laboratory. Biological endpoints will be assessed on samples taken at Visit 0 and Visit 7.

Normal ranges for each value will be provided by the study center. In case of out-of-range values, they may be re-checked upon the Investigator’s judgment.

All laboratory tests will be sampled and analyzed locally. Results of lab tests will be assessed by the Investigator. Abnormal laboratory tests are to be recorded as medical history (Visit 0) or as AEs (Visit 7) only if they are considered clinically significant, that is:

- Symptomatic
- Requiring corrective treatment or additional consultation by relevant specialist
- Leading to study vaccine discontinuation or postponing vaccination
- Meet SAE criteria

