4.4.1.3 Serious Adverse Events

An event will be considered as a serious event if “Yes” is checked for “Serious” in the CRF.

SAEs will be analyzed throughout the study using the following periods:

- Within 7 days after vaccination
- Within 30 days after vaccination
- During the study (i.e., all SAEs occurred during the study)

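### Non-serious laboratory AEs dated to a Visit 7 sample after day 30 appear only in a listing, because the SAP's unsolicited-AE window closes on the first permitted day of that visit and no laboratory table is planned

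*SAP*

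**What the plan says.** Protocol 9.3.3 fixes the laboratory safety sampling for the Russian sites: "Biological endpoints will be assessed on samples taken at Visit 0 and Visit 7". Visit 0 precedes vaccination, so Visit 7 is the only post-vaccination test. Protocol 5.1.4 times it as "Visit 7 (30 [+14] days after Visit 6): Collection of Safety Information, Blood Sampling, and Trial Termination"; Visit 6 carries the 12-month vaccines.

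Results enter the database by one route. Protocol 9.3.3 states: "Abnormal laboratory tests are to be recorded as medical history (Visit 0) or as AEs (Visit 7) only if they are considered clinically significant". Protocol 5.2.6 says that laboratory values "will only be collected in the CRF if they are clinically significant". That section deals with Visit 0 results, but the Synopsis says the same for the panel in general.

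SAP 4.4.1.2.4 defines the analysed unsolicited AEs as "AEs with a time of onset between 0 and 30 days after vaccination or missing". An event with later onset "with a time of onset higher than defined above will not be included in analysis but will be listed separately". SAEs have a whole-study period in SAP 4.4.1.3, "During the study (i.e., all SAEs occurred during the study", and SAP 4.4.1.4 does the same for AESIs. Neither SAP Table 5.1 nor SAP 5.1.3 mentions a laboratory summary.

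**The concern.** The analysis window ends on the first day on which the test may be done. The AE most exposed is one found by the panel itself: an abnormality without symptoms, not serious, but needing treatment or a specialist's opinion. If it is dated to the sample, it is tabulated only when that date is day 30 or earlier. The same finding with a missing start date would be tabulated, while one correctly dated to day 31 would not.

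Group 3 against Group 4 is the trial's only randomised contrast with and without MenACYW. Both groups have the panel, 150 + 75 = 225 children as planned. A reader of the safety tables who sees few or no laboratory AEs has no way to tell that the tables were closed to most permitted test dates.

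**Working it through.** **The plan's own figure.** Neither document gives a number for laboratory findings. The nearest is the detection statement in Protocol 12.5 and SAP 5.5: about 95% for an AE of true incidence 2% with n = 150, the size of Group 3. The formula is 1 − (1 − p)^n, so 1 − 0.98^150 = 95.2%. The figure reproduces.

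**Visit window against analysis window.**
- Visit 7 is day 30 with a window of +14 days and no negative window: days 30 to 44, which is 15 days.
- The analysis window is onset day 0 to 30.
- Days in both: day 30 only, 1/15 = 6.7%. Days outside: 31 to 44, 14/15 = 93.3%.

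These are shares of permitted days. They become shares of findings only if onset equals the sample date and visits are spread evenly over the window. The documents support neither assumption: no rule says whether a laboratory AE starts at sampling, result or first symptom, and the spread of visits is not given. If many visits fall exactly on day 30, the tabulated share is well above 6.7%.

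**Routine tests.** Blood count and chemistry done in routine practice within 7 days before Visit 7 may be used (footnote to the Visit 7 procedures in Protocol 5.1.4). Test days then run from 23 to 44.
- Let the visit be on day 30 + j (j = 0 to 14) and the test k days earlier (k = 0 to 7). The test is on day 30 or before when k ≥ j. That holds for 8 + 7 + … + 1 = 36 of 15 × 8 = 120 combinations, or 30%.
- If the test is always 7 days before the visit, visits on days 30 to 37 qualify: 8/15 = 53%.
- For urine, substitution by a routine test is described only for Visit 0, so Visit 7 urine samples stay on days 30 to 44.

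**What this does to detection.** Take a laboratory AE of 2% incidence in Group 3, with a fraction f of cases falling inside the window. The chance that at least one case is tabulated is 1 − (1 − 0.02f)^150.

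| Assumption | f | Chance of at least one tabulated case |
|---|---|---|
| All cases summarised | 1 | 95% |
| Routine test always 7 days before the visit | 8/15 | 80% |
| Routine test 0 to 7 days before, evenly spread | 0.30 | 59% |
| Sample at the visit, visits evenly spread | 1/15 | 18% |

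The 2% is the plan's own illustrative incidence, not an expected rate of laboratory AEs.

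**The case against.** The strongest reply is that the day-30 limit is not a stray SAP choice. Protocol 9.3.2.2 defines the endpoint as unsolicited AEs up to D30 after each vaccination, and the SAP carries it out. The panel is not among the listed safety endpoints, was added for local practice rather than for a safety concern, and all comparisons are descriptive. This stands, and it is a reason to leave the D0-D30 tables alone. It does not explain why a test scheduled from day 30 onward has no summary of its own.

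A reader might infer that almost every abnormality is left out, or that the tables would show zero whatever was found. The documents do not support that. SAEs and AESIs (which include idiopathic thrombocytopenic purpura) are analysed for the whole study. AEs with missing onset are included. Symptomatic findings may carry an earlier date, and routine tests may date from day 23.

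A reader might also infer that the data are lost. The procedures table does give the unsolicited-AE period as "Collected from D0 to D30 after each vaccination visit", but Protocol 5.1.3 and SAP 3.1 run recording to the next visit, and Protocol 9.3.3 expressly requires Visit 7 laboratory AEs to be recorded. Later events are listed, so this is a reporting gap and the procedures table need not change to capture them.

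Nor is the panel the only objective safety measure: temperature, redness and swelling are measured as well.

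**Conclusion.** The point holds in a limited form. Laboratory AEs that are neither serious nor of special interest, and are dated to a sample after day 30, go to a listing and to no table. This applies to 14 of the 15 permitted Visit 7 days. The proportion of findings affected cannot be obtained from the documents. It approaches 93% only if onset is the sample date and visits are spread evenly, and it falls to 70% or 47% for blood count and chemistry under the two routine-test patterns above. It is lower again if many visits fall on day 30 or symptoms came first. The gap follows from a stated rule, and the risk is that a low or zero tabulated count in Groups 3 and 4 is misread as no abnormalities.

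**What to change.** Add to SAP 4.4.1.2.4 that clinically significant laboratory abnormalities recorded as AEs from the Visit 7 assessment are summarised whatever their onset day, and that their start date is the sample date unless symptoms began earlier.

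Add one descriptive table for Groups 3 and 4: number and percentage of subjects, with 95% Clopper-Pearson interval, having at least one such AE. Use SafAS6 as denominator. Children tested at Visit 7 would be a better denominator, but the documents do not show that a tested/not-tested record exists, so use it only if it does. It should also be checked that AEs detected by the panel can be identified in the database.

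Keep the D0-D30 unsolicited-AE tables unchanged, in line with the protocol endpoint. The cost is two SAP sentences and one extra table, with no new sampling. The reported AE count may rise slightly.
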